# 1. Synopsis

Protocol Title : Usability Analysis of a Novel Bilateral Upper Limb Rehabilitation Device in Post-Stroke Hemiplegia
Study Objectives :
Post-stroke patients commonly experience upper limb impairment, with approximately 85% affected during the acute phase and 40% continuing to experience dysfunction in the chronic phase. Functional upper limb use is essential for daily living and social participation. However, current rehabilitation often requires external assistance or costly robotic devices, which limits accessibility. This study proposes a novel, non-powered mechanical bilateral upper limb rehabilitation system that is easy to don and operate, reduces assistance needs, and allows patients to independently perform rehabilitation exercises. The device aims to improve treatment
accessibility and efficiency while promoting upper limb recovery. The study consists of three
phases: Prototype adjustment; Device fitting and training assessment; Usability and satisfaction evaluation.
Investigational product(s) :
A non-powered, mechanically structured bilateral rehabilitation device designed to facilitate independent upper limb training and enhance rehabilitation accessibility.
Development Phase : I III III IIV Other Not applicable
Study Design :

 
1. ■ Experimental Group : Bilateral upper limb training with the novel device + conventional occupational therapy
 
■ Control Group : □ Placebo
 
□ Study Drug (Name \ Dose \ Usage)
 
■ Other : Upper limb functional training + conventional occupational
 

therapy

 
2. Blinding : ■ Open □ Evaluator-blind □ Single-blind(patient) □ Double-blind(patient+PI)
 
□ Double Dummy □ Other
 
3. Randomization: ■ Yes □ No
 

$4 \blacksquare \text{Parallel design} \square \text{Crossover design} \square \text{Other} \square \text{Not applicable}$
4. Tratalier design Crossover design Conter Not applicable

 
6. Study Period: 1 years (2023/08/01-2024/07/31)
 

6. Dose adjustment : $\Box$ Mandatory $\Box$ Selectively $\Box$ No $\blacksquare$ Not applicable
7. Study location : Single Multi-center Global

 
Endpoints (Outcome measure) :
 
Primary endpoint:
 
Fugl-Meyer Assessment for Upper Extremities (FMA-UE)
 
Secondary endpoint:
 
Brunnstrom stage
 

- Spasticity: Modified Ashworth Scale (MAS)
- Usability: System Usability Scale (SUS)
- Test-retest reliability of repeated training sessions
- User satisfaction: Satisfaction questionnaire

#### Inclusion/Exclusion Criteria:

Inclusion Criteria

- Stroke onset  $\leq 12$  months
- Age 18–70 years
- Stable physiological and neurological status for  $\geq$ 72 hours
- Able to follow at least two-step commands
- Written informed consent obtained
- Unilateral upper limb hemiplegia
- Brunnstrom stage > I (proximal UE)
- MAS < 3 (affected UE)

Exclusion Criteria

- Musculoskeletal impairments preventing device use
- Active, non-healed dermatological lesions

## Study Procedures :

The study employs a novel non-powered bi-manual rehabilitation device based on mechanical transmission principles, specifically designed for upper limb training in post-stroke patients. The device operates through a linear guide rail system that enables the unaffected limb to drive the movement of the affected limb along a mirrored trajectory. This bilateral training approach allows simultaneous motion of both upper limbs, enabling the unaffected side to assist in generating active movement in the hemiplegic arm.

Key features of the device include: (1) bilateral limb synchronization, whereby movement of the unaffected upper limb facilitates motion of the affected limb; (2) a purely mechanical, power-free transmission system utilizing linear rail sliders; and (3) training guided along specific two-dimensional movement trajectories. The device is expected to maintain or improve joint range of motion (ROM), reduce spasticity as measured by the Modified Ashworth Scale (MAS), and promote neuroplasticity in the affected neural pathways.

The structural design centers around a central transmission module that links the motion of the two limbs via linear rails to minimize mechanical resistance. The forearm is secured using an end-effector mechanism, and the device allows for directional movement through longitudinal and lateral rail systems. Different training trajectories can be achieved by varying the patient's seated position, supporting functional training across a range of upper limb motion patterns.

Prior to training, the rehabilitation physician evaluates the affected shoulder and elbow joints using the Brunnstrom Recovery Stage, Fugl-Meyer Assessment for Upper Extremities (FMA-UE), and MAS. Based on MAS scores, patients are stratified into two groups: those with MAS <1 and those with MAS  $\geq$ 1. Participants are then randomly assigned to either the experimental group—receiving bilateral upper limb training with the device combined with conventional occupational therapy—or the control group—receiving only conventional upper limb occupational therapy.

For the experimental group, patients are instructed on how to use the device, and a therapist provides assistance during operation. After the initial session, patients repeat the same training one week later to assess test-retest reliability. Training includes two components: (1) single-joint exercises targeting either the shoulder or elbow, with 20 repetitions per joint for 5 sets, each set separated by a 30-second rest; and (2) dual-joint exercises involving functional movement along rectangular and triangular paths, also conducted in 5 sets of 20 repetitions with similar rest intervals.

Control group training involves conventional functional tasks targeting the affected limb, such as box-pushing (standing or seated), alternating push-pull activities, and use of a hand-cycle. Both groups train for 30 minutes per day, five days a week, for a total of 15 sessions over three weeks. All participants continue their routine rehabilitation treatments throughout the study. At the conclusion of the three-week intervention, the rehabilitation physician reassesses Brunnstrom stage, FMA-UE, and MAS to evaluate functional changes in the affected upper limb.

To assess usability and user satisfaction, both patients and therapists complete the System Usability Scale (SUS) and a satisfaction questionnaire following the training period. The SUS consists of 10 items rated on a five-point Likert scale ranging from "strongly disagree" to "strongly agree." Odd-numbered items are positively worded, while even-numbered items are negatively worded. Scoring involves subtracting 1 from positive item scores and subtracting the original score from 5 for negative items; the total is then multiplied by 2.5 to yield a final SUS score out of 100.

The satisfaction questionnaire assesses five domains—overall satisfaction, comfort, ease of donning the device, perceived improvement in ROM, and rehabilitative assistance—using a five-point Likert-type scale ranging from 1 (very poor) to 5 (very good).

#### 1. **Concomitant Treatments** : Not applicable

**1.** Concomitant Therapy :

**2.** Prohibited Therapy :

1. 2.	Main study Hypothesis : Equality Superiority Non-inferiority
2.	Equivalence Other
2.	
3.	Estimated Sample Size : The planned enrollment for this trial includes 60 stroke patients, with an overall evaluable sample size of 70 individuals. This estimation is based on the recommendation by Lewis and Sauro (2009), who suggest that a minimum of 12 participants is appropriate for usability assessments. In the present study, participants will be categorized into four subgroups based on MAS scores (either <1 or ≥1) and intervention type (experimental or control). To ensure that each subgroup has at least 12 participants, a minimum of 48 participants is required (12 per subgroup). An additional 25% (12 participants) will be recruited to account for potential dropout, bringing the total number of stroke patients to be enrolled to 60. Our center has the capacity to recruit and evaluate all 70 participants. In addition to prospective participants, retrospective data from 60 stroke patients will be included for analysis. Furthermore, a total of 10 individuals—including trained therapists and healthy subjects (such as caregivers or family members who have received prior instruction)— will be included to assess usability and support the study's broader evaluation framework. Efficacy assessment group : Intent-to-treat (ITT) Per-Protocol (PP) Interim analysis : Ves No
5.	Statistical methods :
	Continuous variables will be presented as means with standard deviations, while categorical variables will be expressed as proportions. Independent t-tests will be used to compare continuous variables between groups, and Pearson's chi-square test will be applied for categorical data. One-way analysis of variance (ANOVA) will be employed to assess differences across multiple groups. All statistical analyses will be conducted using the Statistical Package for the Social Sciences (SPSS). A p-value of less than 0.05 will be considered statistically significant.
6.	Handling of Missing Data :
	Only cases with complete datasets will be included in the analysis. Incomplete records will be excluded from statistical evaluation to maintain data integrity.

# 2. Introduction and Rationale

# **2.1 Investigational product(s)**

A non-powered, mechanically structured bilateral rehabilitation device designed to facilitate independent upper limb training and enhance rehabilitation accessibility.

## 2.2 Animal and preclinical study data

Not Applicable

# 2.3 Clinical data

Not Applicable

#### 2.4 Risks / benefits Assessment

During the operation of the equipment, there may be friction and shear effects on the skin, leading to potential skin lesion. Therefore, before conducting rehabilitation programs with the Synslai device, the skin that will touch the device will be covered with a bandage to avoid possible skin damage. Furthermore, risks are held to a minimum due to anonymous coding and keeping all data confidential with no identification to specific participants. No undue stress or uneven medical managements is anticipated as a result of patient's participation. Benefits for the participants is to be able to receive more types and longer time period of post-stroke rehabilitation programs for upper limbs paralysis. It facilitates the functional recovery of post-stroke hemiplegia.

#### 2.5 Regulatory

This study will be conducted in compliance with the protocol approved by the Institutional Review Board, and according to Good Clinical Practice standards. No deviation from the protocol will be implemented without the prior review and approval of the IRB except where it may be necessary to eliminate an immediate hazard to a research subject. In such case, the deviation will be reported to the IRB as soon as possible.

## 3. Objectives and Endpoints

## **3.1 Study Objectives:**

Current rehabilitation strategies for post-stroke upper limb hemiparesis primarily rely on conventional functional training. However, stroke patients often encounter significant barriers to performing such exercises due to muscle weakness, increased muscle tone, and impaired neuromuscular coordination, which frequently necessitate additional physical assistance. While certain rehabilitation devices can help reduce this burden, their high cost limits accessibility and widespread clinical use. To address these challenges, this study proposes a novel bilateral upper limb rehabilitation training program incorporating a non-powered mechanical device. The device is designed with a passive mechanical structure to significantly reduce production and operational costs, while simultaneously minimizing the need for external assistance during training. By combining affordability with functional utility, this approach aims to enhance rehabilitation accessibility and promote upper limb functional recovery in patients with post-stroke hemiplegia.

## 3.2 Study endpoints:

#### 3.2.1 Primary endpoint:

Fugl-Meyer Assessment for Upper Extremities (FMA-UE)

#### **3.2.2 Secondary endpoints:**

Brunnstrom stage

Spasticity: Modified Ashworth Scale (MAS)

Usability: System Usability Scale (SUS)

Test-retest reliability of repeated training sessions

User satisfaction: Satisfaction questionnaire

# 4. Study Design

## 4.1 Overall Design

The study employs a novel non-powered bi-manual rehabilitation device based on mechanical transmission principles, specifically designed for upper limb training in post-stroke

patients. The device operates through a linear guide rail system that enables the unaffected limb to drive the movement of the affected limb along a mirrored trajectory. This bilateral training approach allows simultaneous motion of both upper limbs, enabling the unaffected side to assist in generating active movement in the hemiplegic arm.

Key features of the device include: (1) bilateral limb synchronization, whereby movement of the unaffected upper limb facilitates motion of the affected limb; (2) a purely mechanical, power-free transmission system utilizing linear rail sliders; and (3) training guided along specific two-dimensional movement trajectories. The device is expected to maintain or improve joint range of motion (ROM), reduce spasticity as measured by the Modified Ashworth Scale (MAS), and promote neuroplasticity in the affected neural pathways.

The structural design centers around a central transmission module that links the motion of the two limbs via linear rails to minimize mechanical resistance. The forearm is secured using an end-effector mechanism, and the device allows for directional movement through longitudinal and lateral rail systems. Different training trajectories can be achieved by varying the patient's seated position, supporting functional training across a range of upper limb motion patterns.

Prior to training, the rehabilitation physician evaluates the affected shoulder and elbow joints using the Brunnstrom Recovery Stage, Fugl-Meyer Assessment for Upper Extremities (FMA-UE), and MAS. Based on MAS scores, patients are stratified into two groups: those with MAS <1 and those with MAS  $\geq$ 1. Participants are then randomly assigned to either the experimental group—receiving bilateral upper limb training with the device combined with conventional occupational therapy—or the control group—receiving only conventional upper limb occupational therapy.

For the experimental group, patients are instructed on how to use the device, and a therapist provides assistance during operation. After the initial session, patients repeat the same training one week later to assess test-retest reliability. Training includes two components: (1) single-joint exercises targeting either the shoulder or elbow, with 20 repetitions per joint for 5 sets, each set separated by a 30-second rest; and (2) dual-joint exercises involving functional movement along rectangular and triangular paths, also conducted in 5 sets of 20 repetitions with similar rest intervals.

Control group training involves conventional functional tasks targeting the affected limb, such as box-pushing (standing or seated), alternating push-pull activities, and use of a hand-cycle. Both groups train for 30 minutes per day, five days a week, for a total of 15 sessions over three weeks. All participants continue their routine rehabilitation treatments throughout the study. At the conclusion of the three-week intervention, the rehabilitation physician reassesses Brunnstrom stage, FMA-UE, and MAS to evaluate functional changes in the affected upper limb.

To assess usability and user satisfaction, both patients and therapists complete the System Usability Scale (SUS) and a satisfaction questionnaire following the training period. The SUS consists of 10 items rated on a five-point Likert scale ranging from "strongly disagree" to "strongly agree." Odd-numbered items are positively worded, while even-numbered items are negatively worded. Scoring involves subtracting 1 from positive item scores and subtracting the original score from 5 for negative items; the total is then multiplied by 2.5 to yield a final SUS score out of 100.

The satisfaction questionnaire assesses five domains—overall satisfaction, comfort, ease of donning the device, perceived improvement in ROM, and rehabilitative assistance—using a

five-point Likert-type scale ranging from 1 (very poor) to 5 (very good).

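### No masking is planned for the physician who scores the primary FMA-UE, so rating bias can enter the randomised comparison and could favour the device.

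*Combined protocol and SAP*

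**What the plan says.** The blinding line of the Synopsis reads "Blinding : ■ Open □ Evaluator-blind □ Single-blind(patient", followed by the double-blind options. Only the open box is filled. The form offered evaluator-blinding as a choice of its own, and it was not taken.

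Sections 3.2.1 and 7 name FMA-UE as the primary endpoint. Brunnstrom stage and MAS are secondary.

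Section 4.1 describes the sequence. For the baseline rating, "Prior to training, the rehabilitation physician evaluates the affected shoulder and elbow joints" with all three scales. Patients are stratified by MAS, and then "Participants are then randomly assigned to either the experimental group" or the control group. After the three-week programme, "the rehabilitation physician reassesses Brunnstrom stage, FMA-UE, and MAS". For the device arm, "a therapist provides assistance during operation". The section does not say who delivers the control training.

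The schedule in section 4.3 places the pre-treatment assessment before allocation and shows one post-treatment assessment.

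Section 4.1 also states the hoped-for direction: "The device is expected to maintain or improve joint range of motion (ROM), reduce spasticity as measured by the Modified Ashworth Scale (MAS").

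No section mentions a masked or independent assessor, keeping the allocation from the physician, scoring from video, or a reason for leaving the rater open. Sections 7 and 11.2.1 only list the endpoints by name.

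**The concern.** FMA-UE, MAS and Brunnstrom stage are graded by a clinician watching or handling the limb. A rater who knows the arm, in a study whose protocol expects the device to help, may grade borderline items differently in the two arms. That difference adds directly to the difference in mean FMA-UE. It could affect MAS and Brunnstrom stage as well, because the same physician scores them.

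The planned comparison is an independent t-test at p<0.05 (section 11.2). It cannot tell a rating shift from a treatment effect, and nothing in the plan would detect or remove the shift afterwards.

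Patients and therapists cannot readily be masked to a visible device. The rater is a different matter: the baseline scores are taken before allocation, and no scoring step described in the plan requires knowledge of the arm.

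**Working it through.** **Step 1: the design text set side by side.**

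| Question | What the documents give | Where |
|---|---|---|
| Is the assessor masked? | Open ticked, evaluator-blind unticked | Synopsis |
| Who scores the outcome? | The rehabilitation physician, before and after | 4.1 |
| When is baseline scored? | Before allocation | 4.1, 4.3 |
| Who assists device sessions? | A therapist | 4.1 |
| Who delivers control training? | Not stated | 4.1, 6.1 |
| Does the scorer know the arm? | Not stated; no safeguard described | whole document |

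**Step 2: number of patients.** Section 11.1 has four subgroups of 12, so 4 × 12 = 48. Adding 25% gives 48 + 12 = 60, which reproduces the plan's enrolment figure. The allocation ratio is not stated. Equal subgroups imply 1:1, giving 48/2 = 24 per arm at the minimum and 60/2 = 30 per arm at full enrolment. This count rests on usability; the plan states no FMA-UE effect size, SD or power.

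**Step 3: what a rating shift would do.** Assumptions: no true effect; two-sided test at 0.05 (sidedness is not stated); normal data with equal variances; a rating shift of b standard deviations in favour of the device. The value of b is assumed, because the documents give nothing from which to derive it.

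- Degrees of freedom: 2n − 2, which is 46 for n = 24 and 58 for n = 30. The critical values of t are 2.013 and 2.002.
- Noncentrality: b × √(n/2). For b = 0.2 and n = 24 this is 0.2 × √12 = 0.693. For b = 0.4 and n = 30 it is 0.4 × √15 = 1.549.
- Chance of a false device benefit: the probability that a noncentral t variable exceeds the upper critical value.

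| Assumed shift (SD) | 24 per arm | 30 per arm |
|---|---|---|
| 0 | 2.5% | 2.5% |
| 0.1 | 5.3% | 5.7% |
| 0.2 | 10.0% | 11.5% |
| 0.3 | 17.3% | 20.7% |
| 0.4 | 27.3% | 33.1% |

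The starting value is 2.5% because only results favouring the device are counted. Counting both directions, the rate starts at 5% and reaches 10.4%, 17.4% and 27.4% at 0.2, 0.3 and 0.4 SD with 24 per arm.

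**Step 4: the same in points.** For an assumed shift of 2 FMA-UE points, the chance of a false device benefit at 24 / 30 per arm is 13.3% / 15.7% if the SD is 8, 10.0% / 11.5% if it is 10, and 6.6% / 7.3% if it is 15. These SDs are also assumptions.

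**The case against.** The strongest reply is that an open design is a disclosed choice in a study titled as a usability analysis and sized only for usability. That weakens the point little. FMA-UE is still the declared primary endpoint of a randomised comparison, and usability (SUS) is secondary.

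Other objections stand and limit what can be claimed:

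- **Does the physician know the arm?** A reader might infer so from the open box. The documents never say it, nor that the physician attends sessions. What they support is that no masking is planned or described.
- **Are rating and training fully separate?** A reader might infer that they are. A therapist is named only for device sessions. Recruitment runs through the rehabilitation ward and outpatient department (4.3), so the scorer may also be the treating doctor. Section 9.1 requires each adverse event to be attributed, and whoever does this may need to know the arm.
- **Is a second scorer at hand?** Section 4.1 refers to the rehabilitation physician in the singular. Section 14 mentions clinical doctors and investigators only in connection with data access. No second qualified rater is established, and a change of rater between visits would add variation of its own.
- **Will bias occur, and in one direction?** The stated expectation of benefit makes that plausible; it does not show it.
- **Are the percentages estimates?** No. The plan does not say whether the t-test uses the post-treatment score or the change, so the relevant SD is undefined. Section 4.2 also brings in retrospective data from 60 patients without giving them a role, so 24 or 30 per arm may not be the comparison analysed.

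**Conclusion.** The point holds as a gap in the design. The observer-rated primary endpoint and two secondary endpoints are scored after treatment by a physician for whom no masking is planned, and following the plan as written leaves that source of bias in place. It can enter the comparison and could favour the device.

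The illustrated rise from 2.5% to about 5-27% (24 per arm) or 6-33% (30 per arm) rests on no true effect, 1:1 allocation, a two-sided 5% t-test and an assumed shift of 0.1 to 0.4 SD. It is a sensitivity range and does not predict what this trial will show.

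A reader might also infer that masking the rater would restore the 2.5% exactly. That would require the differential shift to be zero. Patients will still know their arm, and some will reveal it, so masking would reduce the risk without removing it.

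**What to change.** Before any post-treatment scoring takes place:

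1. Change the Synopsis to evaluator-blind and say so in section 4.1.
2. After baseline scoring, have training staff hold the allocation and not disclose it to the scoring physician, who does not attend sessions.
3. Ask patients not to reveal their arm at the post-treatment assessment.
4. Have a team member other than the scorer judge adverse event relatedness.
5. Have the scorer record at the post-treatment assessment whether the arm became known.
6. Where the scorer is also the treating doctor, use another scorer only if one is already on the team and rates that patient at both baseline and follow-up. Otherwise record the rating as unmasked.

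**Cost:** protocol wording and slightly tighter scheduling. Sample size, visits, treatment and endpoints do not change, and no added assessor is required, because item 6 applies only where a second scorer already exists. **Downside:** masking will be incomplete, since some patients will disclose their arm; item 5 makes this visible in the report. **Label:** cheap improvement.

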## 4.3 Schedule of Activities

# Time-Event scheme:

Phase	Recruitment	Pre-treatment	Allocation	Rehabilitation	Post-treatment
		Assessment		programs	Assessment
Evaluation					
Rehabilitation ward /	V				
Outpatient department					
Screening /Administration					
Inclusion / Exclusion criteria	V	V			
Patient profile	V	V			
Assessment					
Brunnstrom stage		V			V
Fugl-Meyer Assessment-Upper		V			V
Extremities (FMA-UE)					
Modified Ashworth scale (MAS)		V			V
Questionnaire					
System Usability Scale (SUS)					V
questionnaire					
Satisfaction questionnaire					V

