# 11. Statistical Considerations

## **11.1 Sample size Determination**

Based on the recommendations by Lewis and Sauro (2009), a minimum of 12 participants per group is considered appropriate for usability testing. In this study, participants will be categorized into four subgroups based on muscle tone classification (MAS < 1 or MAS  $\geq$  1) and treatment allocation (experimental or control group), resulting in a minimum required sample size of 48 (12 participants per subgroup). To account for an anticipated dropout rate of approximately 25%, an additional 12 participants will be recruited, leading to a total target enrollment of 60 stroke patients. In addition, 10 trained healthy participants—including caregivers or family members—will be included for usability assessments and device operation training. The total number of evaluable subjects for the study will therefore be 70.

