#### 11.4 Procedure for accounting for missing, unused and spurious data

The approach to the missing data is to simply omit those cases with the missing data and analyze the remaining data.

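### Patient-rated SUS and satisfaction are collected once, after three weeks of training, with incomplete cases omitted and no rating specified for patients who stop early, so they are at risk of selection bias

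*Combined protocol and SAP*

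**What the plan says.** Section 4.1 and the matching synopsis text set one rating point: "both patients and therapists complete the System Usability Scale (SUS) and a satisfaction questionnaire following the training period". Training runs "for a total of 15 sessions over three weeks". The Time-Event scheme in 4.3 marks SUS and the satisfaction questionnaire in the post-treatment column only. Nothing is marked during the rehabilitation programme, and there is no early-termination visit.

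On missing data, 11.4 states: "The approach to the missing data is to simply omit those cases with the missing data and analyze the remaining data". The synopsis is at least as strict: "Only cases with complete datasets will be included in the analysis". Section 11.2.3 plans no additional analysis, and no sensitivity analysis for missing ratings appears elsewhere.

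On expected losses, 11.1 says: "To account for an anticipated dropout rate of approximately 25%, an additional 12 participants will be recruited". Section 5.3 lists three grounds for withdrawal: loss to follow-up, a new central nervous system lesion, and decompensated systemic disease.

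SUS and satisfaction are secondary endpoints (3.2.2) and FMA-UE is primary (3.2.1). Usability is nevertheless in the title, and the sample size in 4.2 and 11.1 rests on a recommendation for usability testing.

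**The concern.** When the question is whether patients can and will use a device, giving it up is informative. A patient who finds it uncomfortable or hard to put on, and stops for that reason, may leave before the only scheduled rating. The omission rule then removes that patient from the usability result. The summary would describe patients who stayed to the end rather than all patients given the device.

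Comfort and ease of donning are two of the five satisfaction domains in 4.1, and the synopsis presents the device as easy to put on and operate. Patients with the opposite experience would be the most informative about that statement. Section 2.4 also names a device-specific source of discomfort, friction and shear on the skin. A rating not taken when a patient stops cannot be recovered by later analysis.

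**Working it through.** **Inputs from the documents**
- Rating points for SUS and satisfaction: one, after training (4.1, 4.3).
- Minimum of 12 in each of four subgroups, 12 added for dropout, 60 enrolled (4.2, 11.1).
- Incomplete cases omitted (11.4; synopsis, missing data).

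**Assumptions**
- 30 device patients: the allocation ratio is not stated, so 1:1 is assumed.
- Equal dropout in the two arms.
- The completer-stopper gap: the documents give no SUS mean or SD.

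**Step 1. The plan's own figure.** 4 × 12 = 48, and 48 × 1.25 = 60, so the stated enrolment reproduces. The 12 added patients are 12/60 = 20% of those enrolled, although the rate is stated as about 25%. Both fractions are used below.

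**Step 2. Patients who could be unrated.** 0.20 × 30 = 6 and 0.25 × 30 = 7.5, so about 6 to 8 device patients.

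**Step 3. Shift in mean SUS.** Let d be the fraction missing, C the completer mean and S the mean that the missing patients would have given. The all-patient mean is (1 − d)C + dS. The completer mean therefore differs from it by d × (C − S).

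| Assumed gap C − S | d = 0.20 | d = 0.25 |
|---|---|---|
| −10 | −2.0 | −2.5 |
| 0 | 0 | 0 |
| 10 | +2.0 | +2.5 |
| 20 | +4.0 | +5.0 |
| 30 | +6.0 | +7.5 |

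**Step 4. Only some dropouts dissatisfied.** Suppose one third of dropouts would rate 20 points lower and the rest would rate like completers. The shift is then 0.20 × 1/3 × 20 = 1.3 points at 20% missing, or 0.25 × 1/3 × 20 = 1.7 points at 25%.

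**Step 5. Satisfaction items (1 to 5).** Assumed gaps of 0.5, 1 and 2 give +0.10, +0.20 and +0.40 at 20% missing, and +0.125, +0.25 and +0.50 at 25%.

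**Step 6. What complete-case data alone can establish.** Take an assumed completer mean of 70 and let the missing ratings lie anywhere from 0 to 100. At 20% missing, the all-patient mean lies between 0.80 × 70 = 56 and 56 + 0.20 × 100 = 76. At 25% it lies between 0.75 × 70 = 52.5 and 52.5 + 0.25 × 100 = 77.5. Both ranges include values above and below 70, so neither the sign nor the size of the bias is fixed.

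**The case against.** A reader might infer that early stoppers never rate the device and that usability is therefore overstated. The documents do not support either statement as fact.

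- **Attendance.** The plan does not say whether a patient who stops training but remains in the study attends the post-treatment assessment. That is silence, not exclusion. The silence is still a gap, because the synopsis rule, read literally, would drop a returned SUS form if another assessment were missing.
- **Direction.** Upward bias needs stoppers to rate lower than completers. Two of the three withdrawal grounds in 5.3 are medical, with no evident link to usability. Loss to follow-up could conceal dissatisfaction, but the plan does not show that it does.
- **Size.** The allowance covers all causes and both arms, and 12 of 60 is 20%. Treating a full 25% of device patients as dissatisfied stoppers is the upper end.
- **Other raters.** Therapists rate the device, and 4.2 and 11.1 add 10 non-patient participants for usability. Their ratings are not lost through patient dropout in the same way. They do not replace ratings by hemiplegic patients, who are meant to use the device independently.
- **Consequence.** These are secondary endpoints with no stated threshold or decision rule, so no planned conclusion turns on a few points.
- **Timing.** Rating after the planned training is a legitimate choice. Practice before the rating is not itself a flaw.

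All six narrow the point. None supplies a rating for the patient who stops early, or an analysis that shows the effect of its absence.

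**Conclusion.** The concern holds as a risk, not as a demonstrated bias. The scheduled rating comes only after training, incomplete cases are omitted, dropout of 20 to 25% is allowed for, and no rating at discontinuation is specified. Patient-rated SUS and satisfaction are therefore exposed to selection on completion. The direction is probably upward, on the condition that patients who stop would rate the device lower.

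For assumed gaps of 10 to 30 points the shift is about 2 to 7.5 SUS points. It is nearer 1 to 2 if only a third of dropouts differ by 20 points, zero if there is no gap, and negative if the missing patients would have rated higher. The figures rest on the assumed gap and on dropout in the device arm matching the overall allowance. The primary endpoint is not the subject of this point. The change is worth making because usability gives the trial its title and its sample size, and the remedy is cheap.

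**What to change.** - **Sections 4.1 and 4.3.** Have each device-arm patient complete SUS and the satisfaction questionnaire at the last device session attended, whether that is session 15 or the visit at which the patient stops. Mark this in the Time-Event scheme.
- **Section 11.4, and the synopsis to match.** Analyse SUS and satisfaction for every device patient who has a rating, even if that patient's other assessments are missing.
- **Reporting.** Give the number of missing ratings and the reasons, and show completers-only results alongside.
- **Optional.** A rating after the first device session would cover patients who disappear without a recognised last visit. Use it only in a sensitivity analysis, because carrying it into the main result would mix novice with trained use.

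The cost is a few minutes for each patient who stops, a 10-item and a five-domain questionnaire, and amended wording. The headline SUS may be slightly lower. Ratings will come from patients with differing amounts of practice, which is why the completers-only result should stay in view. The bias is removed only to the extent that ratings at stopping are actually obtained.
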